STUDY PROTOCOL

Using Question Prompt Lists during Pediatric Asthma Visits to Increase Adolescent Involvement

NCT02498834

[figure not shown]
April 27, 2015

Study Design/Approach

Study overview: This study is a randomized controlled trial testing the effectiveness of an asthma question prompt list with short video intervention compared to usual care to increase adolescent involvement during visits and improve asthma outcomes. We conducted the study at four pediatric clinics in rural and suburban North Carolina. Forty providers and 359 English- or Spanish-speaking adolescents and their caregivers participated. Adolescents were randomized to the intervention or usual care. Their visits were audio-recorded. Adolescents were interviewed after their visits and their caregivers completed questionnaires. Participants were followed for 12 months.

Study design: This study is a randomized controlled trial testing the effectiveness of an asthma question prompt list with short video intervention compared to usual care to increase adolescent involvement during visits and improve asthma outcomes (ClinicalTrials.gov ID: NCT02498834, protocol ID 14–2628). Figure 1 contains our study protocol.

Figure 1

Study setting: Participants were recruited from four pediatric clinics in suburban and rural areas in North Carolina. Three clinics were private practices and one was an academic practice. Clinics were chosen because they served large numbers of adolescents with persistent asthma from diverse racial/ethnic backgrounds.

Participants: Our target population was adolescents with persistent asthma because we wanted to examine whether we could improve adolescent involvement during visits and asthma outcomes. Our target sample size was 360 adolescents ages 11-17. Research assistants were hired and placed at each clinic.

Clinic staff referred potentially eligible patients who were interested in learning more about the study to a research assistant. During pre-visit wait time, the research assistant explained the study, obtained written caregiver consent and adolescent assent, and administered an eligibility screener. Children were eligible if they were: ages 11 to 17 years; spoke and read English or Spanish; had persistent asthma; were present for an acute or follow-up asthma visit or a well-child visit; and had previously visited the clinic at least once for asthma. Adolescents' caregivers were eligible if they were at least 18 years of age, spoke and read English or Spanish, and were the legal guardian of the adolescent. The research assistant recorded the reasons why individuals declined to participate.

The study statistician prepared the randomization envelopes for the research assistants to use. Adolescents were randomized within providers and opaque envelopes were prepared for the research assistants at each site. A group of envelopes was prepared for each enrolled provider. Eligible adolescents of participating providers were then randomized to the intervention or usual care group. Adolescents in the intervention group watched the video with their caregivers on an iPad. Depending on the clinic, they either watched it in a private area before the visit or they watched it with earphones in the waiting area. The adolescents then received the one-page asthma question prompt list to complete before their visits. Providers were blinded to the adolescent's group assignment. All adolescents' visits were audio-tape recorded. All adolescents were interviewed at baseline after their medical visits by a research assistant while their caregivers completed questionnaires. Research assistants reviewed the caregiver questionnaires before

families left the clinics to ensure data quality. The project manager traveled to the clinics regularly to pick up and review data to ensure quality. Adolescents and caregivers each received \$25 for their time.

Interventions and comparators or controls: Our goal was to increase adolescent involvement during pediatric asthma visits. Adolescents in the intervention group received the asthma question prompt list with video intervention in the clinic before their medical visits. The video was eleven minutes in length and had six themes (asthma triggers, staying active with asthma, how to get mom off your back, tracking asthma symptoms, how to talk to your doctor, and having confidence with asthma). Each theme had its own video that ranged in length from one to two minutes. The final one-page asthma question prompt list had 14 questions about asthma medications, eight questions about triggers and asthma in general, and an area where adolescents could write in questions. The question prompt list took adolescents in the intervention group less than four minutes to complete.

The control intervention was usual care, meaning that the adolescent received no intervention before their medical visits. All adolescent visits were audio-taped and transcribed so we could examine communication during visits.

All audiotapes of the medical visits were transcribed verbatim. Three research assistants were trained to code the transcripts using a detailed coding tool developed and used in prior asthma communication studies. The three coders coded thirty-four of the same transcripts throughout the study period to assess inter-rater reliability.

Study outcomes: Our primary outcomes were (a) asthma control, (b) adolescent asthma management self-efficacy, and (c) asthma quality-of-life at 12 months. Asthma control was measured using the 5-item Asthma Control Test which is a valid and reliable measure of asthma control. Using a 5-point Likert scale, responses are summed to indicate a score ranging from 5 (poor asthma control) to 25 (complete asthma control). Scores above 19 are considered "well controlled", 16 to 19 are considered not well controlled, and scores 15 or below are considered "very poorly controlled." Studies have shown the Asthma Control Test to be reliable, valid, and responsive to temporal changes in asthma control. We measured asthma as being controlled if adolescents scored above 19 on the Asthma Control Test. Adolescent asthma management self-efficacy was measured as a summary score using a 14-item scale that has been shown to have a reliability of 0.87. Prior work in asthma has found asthma management self-efficacy to change in response to an intervention. Adolescent quality-of-life was measured as a mean score on the standardized version of the Juniper pediatric asthma quality-of-life questionnaire. The questionnaire contains 23 items organized in three domains: symptoms, activities, and emotional impact of asthma, and has a reliability of 0.84.

Data collection and sources: After enrollment at baseline, caregivers completed a contact information sheet that contained information on the date of initial contact, the caregiver's name and contact information, including postal address, home/cell number, email address and alternative contact information. The research assistant kept in contact with the patient to determine when their 6- and 12-month follow-up visits would occur. The research assistant called first; if the research assistant could not speak to the caregiver directly she would leave a voice message (caregiver was always asked for permission to leave voice messages during initial meeting). If the research assistant did not hear back from the caregiver within a couple of days she would proceed to text, send an email and/or mail a letter. The research assistant would reach out to the alternative contact as the last resort.

When an adolescent came back to the clinic at the 6-month follow-up visit, their visit was audio-taped, the research assistant interviewed the adolescent, and the caregiver completed a questionnaire. If an adolescent did not have a clinic visit at the 6-month data collection point, the research assistant met the family for a follow-up visit at the location of their choice. If a family withdrew from the study at 6 months, the research assistant recorded the reason why.

If patients did not withdraw from the study, we still attempted to conduct the 12-month follow-up visits. When an adolescent came back to the clinic at the 12-month follow-up visit, their visit was audio-taped, the research assistant interviewed the adolescent, and the caregiver completed a questionnaire. If an adolescent did not have a clinic visit at the 12-month data collection point, the research assistant met the family for a follow-up visit at the location of their choice. If a family withdrew from the study at 12 months, the research assistant recorded the reason why. Adolescents and caregivers each received \$25 at 6 and 12-month follow-up. The adolescent's medical records were reviewed for the period of 12 months before and after the intervention.

Analytical and statistical approaches

Sample Size Calculations: Our planned enrollment was 360 adolescents. We expected a 20% attrition rate over 12 months based on our prior work. Assuming the same attrition rate, 288 patients, or about 144 patients each in the experimental and usual care groups, would complete the study. We expected to go from 50% of the adolescents in the intervention group being well controlled according to the Asthma Control Test at baseline to 70% of adolescents in the intervention group being well controlled at 12 months. An intervention study conducted with adults with asthma found that an educational intervention increased the percent of adults controlled according to the Asthma Control Test from 50% to 65% over a 6-month period. From past studies, we expected an average self-efficacy score of around 3.7 to 3.8 and average quality of life scores of 5.7 to 5.8 for the adolescents. With 143 families in each group and an expected increase of 20% in asthma control, as well as an expected increase in adolescent self-efficacy and adolescent's quality of life by at least one half of a point, which equates to effect sizes of 0.45 to 0.6, the study is powered at 80% with a type I error rate of 5% for each of the between-group differences for these outcome variables. Our estimates for the control group come from our prior work.

Analytical Approach: All analyses were performed using SPSS. Generalized estimating equations, (i.e., the GEE method) were used to analyze the data, which allowed families to be nested within providers. The GEE method was used to detect clinically significant differences in our primary outcome variables: asthma control, adolescent self-efficacy in asthma management, and adolescent quality-of-life. Primary analysis used the 12-month follow-up data. Our multivariable models for the primary outcomes were nested by provider and included several covariates. For all of our models, we examined relevant interaction terms. For scale items that were missing, we imputed missing scale items using overall sample mean scores.

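### Does the plan lose its stated goal, adolescent involvement in the visit, by naming only three 12-month asthma outcomes?

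*Combined protocol and SAP*

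**What the plan says.** Involvement is prominent. The title is "Using Question Prompt Lists during Pediatric Asthma Visits to Increase Adolescent Involvement". Under Participants, the target population is justified because "we wanted to examine whether we could improve adolescent involvement during visits and asthma outcomes". Under Interventions and comparators or controls, the plan states: "Our goal was to increase adolescent involvement during pediatric asthma visits".

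The outcome text is narrower. Study outcomes reads: "Our primary outcomes were (a) asthma control, (b) adolescent asthma management self-efficacy, and (c) asthma quality-of-life at 12 months". It lists no secondary outcome. Sample Size Calculations claims 80% power "for each of the between-group differences for these outcome variables", meaning the same three. Analytical Approach adds: "The GEE method was used to detect clinically significant differences in our primary outcome variables", and bases the primary analysis on 12-month data.

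On the visit itself, Participants says "All adolescents' visits were audio-tape recorded". The interventions section gives the purpose: "All adolescent visits were audio-taped and transcribed so we could examine communication during visits". Three trained research assistants coded the transcripts with a tool from earlier asthma communication studies, and all three coded the same 34 transcripts to check agreement.

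**The concern.** A reader who starts from the title expects a randomised answer to one question: did the prompt list and video make adolescents more active in the visit? The outcome, power and analysis sections do not say which coded item would answer it, at which visit, or how the arms would be compared.

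Two things could be at stake. First, the intervention is meant to work through the visit. Without an involvement result, a null 12-month finding could mean that the visit did not change, or that it changed and asthma did not. A positive finding could not be tied to the intended mechanism. Second, a detailed coding tool can yield many items, and an unnamed item leaves room to choose one after the results are seen.

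**Working it through.** **What is named and what is not**

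| Element | Visible text | Where |
|---|---|---|
| Goal of involvement | Stated | Title; Study overview; Study design; Participants; Interventions and comparators or controls |
| Recording and transcription | Stated, for all adolescents' visits | Participants; Interventions and comparators or controls |
| Coding tool and agreement check | Stated; 34 transcripts coded by all three coders | Interventions and comparators or controls |
| Method that handles providers | GEE, introduced for the data in general | Analytical Approach |
| Coded item, visit, arm comparison | Not named | – |
| Figure 1, described as containing the study protocol | Not shown in this copy | Study design |

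The gap is therefore one definition and one comparison. The data and the method are both there. Analytical Approach first introduces GEE for the data as a whole, then itemises the primary outcomes, and later speaks of all the models. So it does not confine GEE to the three primary outcomes.

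**The plan's own figures**

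- Attrition: 360 × (1 − 0.20) = 288, or 144 per arm. This reproduces.
- Power for asthma control: 143 per arm, 70% in the intervention arm. No 12-month control rate is stated; assume 50%. A two-sided 5% pooled z-test gives 93.6%.
- Power for the two scores at 143 per arm: 96.7% at an effect size of 0.45, and 99.9% at 0.6.

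The stated 80% is therefore a floor on these inputs. It has no bearing on involvement, for which the documents give no measure, expected difference or standard deviation.

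**Could the existing recordings support an involvement result?**

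Inputs: 359 adolescents (Study overview). Assumptions: a 180/179 split, a yes/no item at the first visit, and usual-care rates of 10% to 50%.

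Power of the pooled z-test is Φ[(|p₂ − p₁| − 1.96·s₀)/s₁], with s₀ = √[p̄(1 − p̄)(1/n₁ + 1/n₂)] and s₁ = √[p₁(1 − p₁)/n₁ + p₂(1 − p₂)/n₂].

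Example, 30% vs 44.2%:

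- p̄ = (180 × 0.30 + 179 × 0.442)/359 = 0.371
- s₀ = 0.0510 and s₁ = 0.0504
- (0.142 − 1.96 × 0.0510)/0.0504 = 0.83, so power is 80%

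The half-width of the 95% interval at equal rates is 1.96·√[p(1 − p)(1/180 + 1/179)]. At 30% this is 1.96 × 0.0484 = 9.5 points.

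| Usual-care rate (assumed) | Detectable rate, 180/179 | Difference (points) | Difference with 10% of recordings unusable (assumed), 162/161 | 95% half-width, 180/179 |
|---|---|---|---|---|
| 10% | 20.6% | 10.6 | 11.3 | 6.2 |
| 15% | 27.0% | 12.0 | 12.7 | 7.4 |
| 30% | 44.2% | 14.2 | 15.0 | 9.5 |
| 50% | 64.6% | 14.6 | 15.4 | 10.3 |

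The z-test ignores providers, so it was checked by simulation: 40 providers with about 9 adolescents each, 1:1 within provider, logit GEE with exchangeable correlation, and assumed latent-scale intraclass correlations of 0, 0.05 and 0.10. Power was 79% to 83% at three of the contrasts above. With 30% in both arms, rejection was 4% to 6%. Clustering does not undo the z-test figures, because allocation is within provider.

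For a continuous score at the first visit, the detectable standardised difference is (1.96 + 0.84)·√(2/179.5) = 0.30.

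**The case for a change.** The strongest case for a change is that saying communication will be examined does not define an outcome. The goal is stated repeatedly, the tapes were made to study communication, and a few sentences naming one secondary item at the first visit would cost almost nothing. The first visit suits this best, because taping at 6 and 12 months is described only for those who came back to the clinic. On this view, an unnamed item invites selection and the trial gives up its most direct evidence on mechanism.

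Part of this stands. The visible text does not name the item, and any involvement result would have to be read as supportive.

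The rest carries less weight:

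- The visible text names no secondary endpoint of any kind, although it also describes 6-month interviews, caregiver questionnaires and a medical-record review. Its silence on involvement is therefore not specific to involvement.
- The documents join two purposes and do not rank them. The goal sentence sits in the description of the intervention. Taking 12-month health outcomes as primary, with involvement as the process leading to them, is a legitimate design.
- A suggested item, such as whether the adolescent asked any asthma question, may not be in the coding tool. It also comes close to checking that a list of questions was used.
- The text is in the past tense with 359 enrolled. An item added now could well be post hoc, so it would do little to limit selection.

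**Conclusion.** No change to the plan follows. The observation is accurate as far as it goes: the visible text names neither the involvement measure nor its arm comparison. But this is detail that competent analysts would supply from what is already in place, namely recorded and coded visits, a reliability check and a provider-nested GEE. It may also be defined in the figure or the coding tool, which cannot be seen here.

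The three primary outcomes, their power and their conclusions are untouched. No harm can be quantified. The detectable differences of about 11 to 15 points show only that the first-visit recordings are adequate for a supportive result. They rest on an assumed 180/179 split, assumed usual-care rates of 10% to 50%, and at most 10% of recordings lost. They do not allow for carry-over between arms through shared providers, which could shrink a difference in visit communication.

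### A research assistant who may know the arm interviews adolescents for all three self-reported primary outcomes; self-completion would remove the interviewer's part of any bias

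*Combined protocol and SAP*

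**What the plan says.** All places are in the combined protocol and SAP.

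- **Allocation (Participants).** "Research assistants were hired and placed at each clinic". On the envelopes, the plan says: "The study statistician prepared the randomization envelopes for the research assistants to use". Allocation was by individual adolescent within provider, using opaque envelopes supplied to the assistants on site.
- **Visible difference between arms (Participants).** "Adolescents in the intervention group watched the video with their caregivers on an iPad", and they then receive the prompt list. Under Interventions and comparators or controls, usual care gets nothing before the visit.
- **Blinding (Participants).** "Providers were blinded to the adolescent's group assignment". Nothing is said about research assistants or outcome interviewers.
- **Baseline data (Participants).** "All adolescents were interviewed at baseline after their medical visits by a research assistant while their caregivers completed questionnaires". Assistants check the caregivers' forms before the family leaves.
- **Follow-up data (Data collection and sources).** At 6 and 12 months, "the research assistant interviewed the adolescent, and the caregiver completed a questionnaire". Where there is no clinic visit, "the research assistant met the family for a follow-up visit at the location of their choice". The research assistant also keeps in touch with the family to arrange these visits.
- **Primary outcomes (Study outcomes).** There are three at 12 months: control on the 5-item Asthma Control Test (a score above 19), a 14-item self-efficacy scale, and a 23-item quality-of-life questionnaire. All are answered by the adolescent. The section does not say how they are administered.

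**The concern.** The role that uses the envelopes is also the role that interviews the adolescent. The interviewer may know the arm, and every primary outcome is a subjective answer. Opaque envelopes protect concealment before allocation, and provider blinding protects the visit. Neither protects the measurement of outcome.

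The same exposure applies to all three outcomes, so agreement among them would not be independent confirmation. Some video themes (tracking symptoms, having confidence with asthma) lie close to what the scales ask, so an adolescent answering someone thought to know about the video has a plausible reason to report more confidence and control. The baseline interview follows the visit, and so also follows allocation and the video. A baseline score gathered this way is open to the same influence.

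Adolescents cannot be blinded. The added influence of an interviewer who may know the arm is avoidable.

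**Working it through.** **1. Who does what.** The role and blinding questions need no arithmetic.

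| Step | Who, according to the plan | Stated to be blinded? |
|---|---|---|
| Prepares envelopes | Study statistician | Not stated |
| Uses envelopes on site | Research assistants | Not stated |
| Gives out video and prompt list | Not stated | Not stated |
| Conducts the medical visit | Provider | Yes |
| Interviews adolescent at baseline, 6 and 12 months | A research assistant | Not stated |
| Completes caregiver questionnaire | Caregiver, alone | Not applicable |

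Apart from the interview, the only described sources of adolescent data are the visit recordings and the medical record review. Neither can yield the three scale scores. It is therefore an inference, though a strong one, that the scales are collected at the interview.

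**2. The plan's own figures (Sample Size Calculations).** Attrition reproduces: 360 × 0.80 = 288, or 144 per group. The plan then uses 143. The stated 80% power does not reproduce, except as a floor:

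- 50% vs 70%, n = 143 per group: SE under the null = √(2 × 0.60 × 0.40/143) = 0.0579; SE under the alternative = √((0.25 + 0.21)/143) = 0.0567; power = Φ((0.20 − 1.96 × 0.0579)/0.0567) = 93.6%.
- Effect size 0.45: Φ(0.45/√(2/143) − 1.96) = 96.7%. Effect size 0.6: 99.9%.

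This gap does not bear on the present point. Only n = 143 is carried forward.

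**3. Illustration: what a reporting shift would do.** The inputs are 143 per arm (from the plan), a 5% type I error per outcome (from the plan; two-sided is assumed), 50% controlled in both arms (assumed, since the plan gives 50% only as the intervention group's baseline) and a true effect of zero. The shift *b* between arms is assumed throughout.

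Rejection probability = P(|Z + b/SE| > 1.96), with

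- proportion: SE = √(2 × 0.25/143) = 0.0591;
- scale, in SD units: SE = √(2/143) = 0.118.

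For a 5-point shift, b/SE = 0.05/0.0591 = 0.846. The upper tail beyond 1.96 − 0.846 = 1.114 is 0.133 and the lower tail is about 0.002, which gives 13.5%.

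| Shift in % controlled | False-positive rate | Shift on a scale | False-positive rate |
|---|---|---|---|
| 0 | 5.0% | 0 | 5.0% |
| 3 points | 8.0% | 0.05 SD | 7.1% |
| 5 points | 13.5% | 0.10 SD | 13.5% |
| 8 points | 27.2% | 0.15 SD | 24.5% |
| 10 points | 39.4% | 0.20 SD | 39.4% |

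Letting the variance of the proportion change with the shift gives 27.3% and 39.7% at 8 and 10 points. Against the planned effects, 10 points is half of 20, and 0.20 SD is 0.20/0.45 = 44% of the smaller planned effect size.

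The calculation is an unadjusted two-sample approximation. The plan uses GEE with covariates and nesting by provider.

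**The case against.** Several stronger readings are tempting, and the documents do not support them.

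- **One person did everything.** A reader might infer that the same individual opened the envelope, handed over the video and list, and interviewed the family a year later. The text names a role and not a continuing individual, and it does not say who delivered the intervention. A different interviewer who did not know the arm is not excluded; none is described.
- **The scales were read aloud.** The plan says adolescents were interviewed. It does not say that the items were asked orally, and it calls the quality-of-life instrument a questionnaire. Self-completion during the session is possible.
- **The bias favours the intervention by a known amount.** Neither direction nor size can be derived. The Asthma Control Test has fixed response options, the exposure was an 11-minute video and a one-page list, and the primary data come 12 months later. Whether an assistant would still recall the arm is unknown.
- **The trial's false-positive rate is 13.5% or 39%.** Those figures follow from assumed shifts and would fit any trial of this size. They also cannot separate the interviewer's influence from the unblinded adolescents' own reporting, which self-completion leaves in place. They do not measure what the fix would gain.

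All four limits stand. They reduce certainty about how large the problem is. They do not supply the missing safeguard: the plan describes no protection for outcome assessment on any primary outcome.

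A practical objection also stands in part. The text is written as completed conduct, with 359 adolescents enrolled and followed, so a change of procedure may come too late.

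**Conclusion.** The concern holds as a weakness in the measurement procedure. Research assistants use the envelopes, a research assistant interviews the adolescent at all three time points, blinding is stated only for providers, and no other route is described for collecting the three self-reported primary outcomes. An interviewer who may know the arm could influence all of them.

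The size and direction of any bias cannot be obtained from the documents; a bias towards the intervention is plausible and no more than that. The false-positive figures are illustrations under assumed shifts. The conclusion rests on one inference, that the scales were collected at the interview, and on the absence of any description of a blinded assessor. It is a change that should be made, held with medium confidence. It is not evidence that the trial's result is biased.

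**What to change.** In the Participants and Data collection and sources sections, specify that adolescents in both arms complete the Asthma Control Test, self-efficacy and quality-of-life items themselves at baseline, 6 and 12 months. Use paper, or the iPad where one is available; paper also serves visits held away from the clinic. The research assistant checks only for skipped items and does not read out or score them.

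The change needs form set-up but no new staff. Eligibility already requires adolescents to read English or Spanish, the intervention arm already fills in a one-page list, and assistants already check caregivers' self-completed forms. The three instruments total 5 + 14 + 23 = 42 items.

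The cost is possibly more skipped items, or slower completion, in the youngest adolescents. Skipped items matter because Analytical Approach fills missing scale items with overall sample means. The completeness check limits this. The change removes only the interviewer's part of the bias, since adolescents still know their arm.

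If data collection is already complete, report who conducted the 12-month interviews, whether they knew the arm and how each scale was given, and state any lack of assessor blinding as a limitation on the conclusion.

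### Three unranked primary outcomes each carry a 5% type I error rate, with no multiplicity adjustment, testing order or rule for which results support a claim of benefit

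*Combined protocol and SAP*

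**What the plan says.** The section on study outcomes gives the primary set: "Our primary outcomes were (a) asthma control, (b) adolescent asthma management self-efficacy, and (c) asthma quality-of-life at 12 months". The letters label the outcomes; no text makes them a rank or a testing sequence.

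The only test level in the document is in Sample Size Calculations, which claims 80% power with "a type I error rate of 5% for each of the between-group differences for these outcome variables". It does not say whether the tests are one- or two-sided.

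The Analytical Approach treats the three outcomes alike: "The GEE method was used to detect clinically significant differences in our primary outcome variables". It goes on to say "Our multivariable models for the primary outcomes were nested by provider and included several covariates". It gives no significance level, adjustment, alpha split or hierarchy, and does not say how many outcomes must succeed. No other section supplies these.

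**The concern.** With several primary outcomes, the error rate of an overall conclusion depends on the rule that links the separate tests to it. Three rules are compatible with the text, and they have different error properties:

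- **Any one outcome suffices.** Three tests at 5% give a familywise error above 5% whenever two or three of the nulls are true.
- **All three must succeed.** The overall error cannot exceed 5%, and no adjustment is needed.
- **Three separate, outcome-specific claims.** Each claim has its own 5%, and nothing controls the error across the set.

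The plan does not choose among them. What is at stake is how a mixed result should be read, for example one significant outcome out of three. It could be a positive trial, a negative trial or one isolated finding, and the document gives no basis for deciding.

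**Working it through.** **Inputs from the document.** Three primary outcomes; 5% and 80% power for each; 143 families per group; effect sizes of 0.45 to 0.6 for self-efficacy and quality of life; enrolment of 360 with 20% attrition. For asthma control the plan expects a rise from 50% at baseline to "70% of adolescents in the intervention group being well controlled at 12 months".

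**Assumptions, because the document is silent.** Two-sided tests; a 50% control-group rate at 12 months; equal correlation ρ between the three test statistics, varied from 0 to 0.9.

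**Step 1. The plan's own figures.** Completers: 360 × 0.80 = 288, or 144 per group (the power sentence uses 143). The 80% power does not reproduce; simple tests give more.

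- Asthma control, 50% v 70%, pooled z-test: (0.20 × √143 − 1.960 × √(2 × 0.6 × 0.4)) / √(0.25 + 0.21) = (2.392 − 1.358) / 0.678 = 1.524, so power is 93.6%.
- Effect size 0.45: noncentrality 0.45 × √(143/2) = 3.805; two-sample t-test power is 96.7%.

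The 80% can be read as a minimum, since 143 per group gives 80% at an effect size of 2.802 × √(2/143) = 0.33. The error rates below do not use the power figure.

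**Step 2. Error if any one outcome suffices.** With independent tests and all three nulls true, 1 − 0.95³ = 0.1426. With two nulls true, 1 − 0.95² = 0.0975. For correlated tests with all nulls true, the rate is 1 − P(all |Z| ≤ 1.960) for three equicorrelated standard normals, found by numerical integration. The two-null correlated figures are simulated (1,000,000 draws).

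| ρ | Three nulls true | Two nulls true |
|---|---|---|
| 0 | 14.3% | 9.8% |
| 0.5 | 12.5% | – |
| 0.7 | 10.9% | 8.3% |
| 0.8 | 9.8% | – |
| 0.9 | 8.4% | 7.0% |

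Sidedness matters little: one-sided 5% tests leave 14.3% unchanged at ρ = 0 and give 8.0% at ρ = 0.9.

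**Step 3. Error if all three must succeed.** With all nulls true: 0.05³ = 0.01% at ρ = 0; by simulation, 0.9% at 0.7 and 2.3% at 0.9. Under any mix of true and false nulls the bound is 5% (intersection-union argument).

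**Step 4. Error under Holm.** With all nulls true, Holm rejects something only if the smallest p-value is at most 0.05/3 = 0.0167. The rate is 1 − (1 − 0.0167)³ = 4.9% at ρ = 0, 3.9% at 0.7 and 3.0% at 0.9.

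**Step 5. Power at the strictest Holm step** (alpha 0.0167, critical value 2.394).

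- Asthma control: (2.392 − 2.394 × 0.693) / 0.678 = 1.081, so power is 86.0%.
- Effect size 0.45: t-test power is 91.8%.
- If unadjusted power were exactly the stated 80%: noncentrality 1.960 + 0.842 = 2.802; 2.802 − 2.394 = 0.408, so power is about 66%. Holm does better when other outcomes also respond: if all three have 80% unadjusted power, power per outcome is 73% to 75% (simulated, ρ from 0.7 to 0).

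These power figures come from simple two-sample tests, not the planned GEE models with covariates.

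**The case against.** The strongest defence is that the sample-size sentence assigns 5% to each difference because three separate questions are being asked. On that reading there is no single claim to protect, and whether familywise control is needed is debatable. This is a legitimate position, but the document does not state it, and the study overview gives one broad aim of improving asthma outcomes. The defence therefore shows one rule that the plan could have adopted, not one that it did.

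The outcomes may also be correlated: the quality-of-life questionnaire has a symptoms domain that plausibly overlaps with the Asthma Control Test. That makes 14.3% an upper value, but even at an assumed correlation of 0.9 the rate is 8.4%.

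The text is in the past tense and reports completed participation ("Forty providers and 359 English- or Spanish-speaking adolescents and their caregivers participated"), so a rule added now may be post hoc. That limits what a change can achieve. It does not remove the ambiguity, and adjusted values need only the three p-values.

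Two stronger readings are tempting. A reader might infer that the plan permits a claim of benefit on whichever outcome reaches p<0.05, so that the trial's error rate is 14.3%. The document contains no claim rule and no such criterion, and silence is not permission.

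A reader might also infer from the nesting by provider that clustering reduces power to about 80%, making an adjustment expensive. But the text on randomisation says that adolescents were allocated within providers. Both arms occur under each provider, so provider differences largely cancel from the treatment contrast, and a cluster-trial design effect does not apply. Treatment effects that vary between providers, or imbalance within them, could cost some power, but the document gives nothing from which to quantify this.

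**Conclusion.** The point holds as a gap in the plan: three unranked primary outcomes, 5% for each, and no adjustment, order or success rule. The error rate of an overall claim of benefit is therefore undefined. It is 8.4% to 14.3% if any one outcome suffices and all three nulls are true, at most 5% if all three are required, and 5% per claim without familywise control if the claims are separate. The range rests on assumed correlations of 0 to 0.9 and two-sided tests. The gap affects what may be claimed from the results; it does not invalidate the data or the individual outcome estimates. It should be fixed.

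**What to change.** State the success rule first: any one outcome, all three, or three separate claims. Unless all three are required, test the three outcomes with the Holm procedure at familywise two-sided 5%, report adjusted p-values beside the unadjusted ones, and base any overall claim of benefit on the adjusted values. In Sample Size Calculations, say that 5% is the unadjusted per-outcome level and give power at alpha 0.0167. If the adjustment is added after the results were known, label it post hoc.

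The cost is a few sentences and some power, with no extra patients or data. On the plan's own effects and an assumed 50% control rate, strictest-step power falls from 93.6% to 86.0% for asthma control and from 96.7% to 91.8% at effect size 0.45, still above the stated 80%. If unadjusted power were exactly 80%, it would fall to about 66%. An all-three rule avoids adjustment but also costs power: with 80% per outcome and independent tests, 0.80³ = 51.2%, and more if the tests are positively correlated.
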